### **9.3 Clinical Laboratory Data**

For each clinical laboratory test items, the descriptive statistics for measured values at each timepoint and changes from baseline will be summarized for each treatment group. Shift tables will be produced for assessing changes from baseline in status (low/normal/high in accordance with the reference range) for each treatment group. For qualitative urinalysis, shift tables of changes from baseline will be produced for each treatment group.

The data on Visit 1 (Day -14 to 0) is defined as baseline for all treatment groups.

The potential Hy's Law Cases (any increase of aspartate aminotransferase [AST] or alanine aminotransferase [ALT] of  $\geq 3$  times the upper normal limit or screening value with an increase in total bilirubin of  $\geq 2$  times the upper normal limit or screening value) will be listed by subject.

### **9.4 Vital Sign Data**

The descriptive statistics of measured values at each timepoint and changes from baseline will be summarized by treatment group.

The data on Visit 1 (Day -14 to 0) is defined as baseline for all treatment groups.

### **9.5 Physical Examination Data**

Physical examination (PE) findings will be listed by subject. For body weight, the descriptive statistics of measured value at each timepoint and changes from baseline will be summarized by treatment group.

The data on Visit 1 (Day -14 to 0) is defined as baseline for all treatment groups.

### **9.6 Electrocardiogram Data**

Shift table of abnormality in electrocardiogram (ECG) findings will be produced for each treatment group.

The data on Visit 1 (Day -14 to 0) is defined as baseline for all treatment groups.

## **10 Pharmacokinetic Analyses**

There are no pharmacokinetic analyses in this trial.

## **11 Pharmacodynamic Analyses**

### **11.1 Statistical Analyses of Primary Pharmacodynamic Endpoints**

#### **11.1.1 Inhibition of Platelet Aggregation**

- 1) Equivalence will be indicated if the 95% confidence interval (CI) for the ratio (Test/Reference) of the IPA is contained within the equivalence limits of 0.70 to 1.43 for each parameter of platelet aggregation.

Primary Analysis will be performed on the natural-log transformed IPA. The mixed-effect linear model for each parameter will include a term for treatment regimen as a fixed effect, and a term for subject as a random effect. From each analysis, the least squares treatment means and difference (T - R) and the 95% CI for the treatment difference will be obtained. Then, the antilogs of the difference and the confidence limits will provide the estimate and 95% CI for the ratio (T/R) of the geometric means of platelet aggregation parameters of the test and reference.

This method will be used to compare drugs/combinations, ie, cilostazol/clopidogrel vs clopidogrel alone; cilostazol/ASA vs ASA alone, as well as the different genotype combinations.

For the not log-transformed data, the same analyses will be conducted exploratory.

- 2) The IPA of each treatment regimen will be summarized using the descriptive statistics. The means for the treatment difference (T-R) and their 95 % CI will be calculated.

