## 2 Trial Objectives

The primary objective of this trial is to determine the effects of orally administered cilostazol 100 mg twice daily, Acetylsalicylic acid (ASA) 100 mg once daily or clopidogrel 75 mg once daily alone as well as in combination of cilostazol 100 mg twice daily/ clopidogrel 75 mg once daily or cilostazol 100 mg twice daily/ ASA 100 mg once daily on ex-vivo platelet function testing.

A key secondary objective is the effect of orally administered cilostazol 100 mg twice daily, ASA 100 mg once daily or clopidogrel 75 mg once daily alone as well as in combination of Cilostazol 100 mg twice daily/ clopidogrel 75 mg once daily or cilostazol 100 mg twice daily/ ASA 100 mg once daily on bleeding time in healthy subjects. While bleeding time is an important parameter in this regard it also does exhibit a higher level of intra- as well as interindividual variability and an additional tissue dependent variability. Therefore, bleeding time is evaluated as a key secondary parameter.

In addition, the effects of a combined administration of cilostazol 100 mg twice daily/ clopidogrel 75 mg once daily in subjects with a homozygous wildtype allele of *CYP2C19* (\*1/\*1) showing normal *CYP2C19* activity will be compared with the effects of subjects carrying either the heterozygous *CYP2C19* (\*1/\*2) isoform and with subjects carrying the homozygous *CYP2C19* (\*2/\*2) isoforms, displaying a intermediate and poor *CYP2C19* activity, respectively.

A further secondary objective is to assess the safety variables after the orally administration of cilostazol 100 mg twice daily, ASA 100 mg once daily or clopidogrel 75 mg once daily alone as well as a combination of cilostazol 100 mg twice daily/ clopidogrel 75 mg once daily or cilostazol 100 mg twice daily/ ASA 100 mg once daily.

[figure not shown]

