## **5.5 Handling of Missing Data**

No data imputation will be performed for missing data in this trial.

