# **6 Primary and Secondary Outcome Variables**

## **6.1 Primary Outcome Variables**

The primary analysis variable of the trial is ex-vivo inhibition of platelet aggregation (IPA).

- Ex-vivo platelet function: primary parameters to be determined in citrated platelet rich plasma (PRP) by
  - Light transmission aggregometry (5  $\mu$ M ADP, residual aggregation at 5 minutes)
  - Light transmission aggregometry (Arachidonic acid 500 mg/L, residual aggregation at 5 minutes)

For individual subjects, IPA is defined as the percentage decrease of platelet aggregation of stimulated plasma before and after treatments with trial medications.

$$\text{IPA (\%)} = 100 \times (\text{platelet aggregation at baseline} - \text{platelet aggregation after treatment}) / \text{platelet aggregation at baseline}$$

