### **11.2 Statistical Analyses of Secondary Pharmacodynamics Endpoints**

#### **11.2.1 Inhibition of Platelet Aggregation**

IPA calculated from the light transmission aggregometry in PRP (20  $\mu$ M ADP, residual aggregation at 5 minutes) will also be analysed using the methodology specified in [Section 11.1.1](#).

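### Section 11.1.1 decides equivalence on ln(IPA), which does not exist when IPA is zero or negative, and the SAP has no rule for such values

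*SAP*

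**What the plan says.** - **Endpoint (SAP 6.1).** "IPA is defined as the percentage decrease of platelet aggregation of stimulated plasma before and after treatments with trial medications". The formula is 100 × (baseline − after treatment) / baseline. It has no lower bound.
- **Deciding analysis (SAP 11.1.1).** "Primary Analysis will be performed on the natural-log transformed IPA". Equivalence is declared if the 95% CI for the Test/Reference ratio, back-transformed from a mixed model, lies within 0.70 to 1.43.
- **Reach.** The method serves clopidogrel and ASA with and without cilostazol, "as well as the different genotype combinations". Section 2 gives the genotype objective: the combination's effects in wildtype subjects "will be compared with the effects of subjects carrying either the heterozygous" and the homozygous variant. Section 11.2.1 extends the method to 20 µM ADP: "residual aggregation at 5 minutes) will also be analysed using the methodology specified in" Section 11.1.1.
- **Untransformed IPA (SAP 11.1.1).** "For the not log-transformed data, the same analyses will be conducted exploratory". A descriptive summary is also planned: "The means for the treatment difference (T-R) and their 95 % CI will be calculated".
- **Missing data (SAP 5.5).** "No data imputation will be performed for missing data in this trial".
- **Analysis set (SAP 5.4).** Subjects who complete both the reference-alone and the combination period are included.
- **Changes (SAP 14).** Only the ECG summary and a dropped sensitivity analysis are listed.

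**The concern.** The primary analysis is undefined on part of the range that its own endpoint allows. A subject whose aggregation does not fall below baseline has an IPA of, say, −5%. That is a measurement, not a missing value, so Section 5.5 does not cover it. Section 5.4 says which subjects enter, not which of their records can be used.

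Software will normally drop a record whose log is undefined. That is an unstated exclusion, and it falls only on the records with least inhibition. The other course is a floor or an added constant chosen ad hoc. On the log scale a small floor becomes an extreme value, so one record in 17 can settle the verdict.

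The untransformed analysis does not fill the gap. It is exploratory, and as written it yields a T−R difference, to which the ratio limits 0.70 to 1.43 cannot be applied.

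**Working it through.** **1. The plan's own figure.** Inputs from Section 4: true ratio 1, SD 27%, limits 0.70 to 1.43, 95% CI, 17 per group, 90% power. Reading 27% as within-subject, the SD of a paired log difference is √2 × 0.27 = 0.382, or √2 × √ln(1 + 0.27²) = 0.375. Paired equivalence power at n = 17 is 0.902 or 0.915, so 17 and 90% reproduce. The calculation assumes 17 usable pairs. With 16, power is 0.875 or 0.889.

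**2. One undefined value.** Take 16 pairs with mean log ratio 0 and SD 0.375, plus one subject with reference IPA ≤ 0 and an assumed test IPA of 20%.

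- Pair excluded: half-width 2.131 × 0.375/√16 = 0.200, so the ratio is 1.00 (0.82 to 1.22). Equivalent.
- Value set to 5%: the added difference is ln(20/5) = 1.386, giving 1.09 (0.84 to 1.40). Equivalent.
- Value set to 2%: 1.15 (0.81 to 1.61). Not equivalent.
- Value set to 1%: the added difference is ln(20) = 2.996 and the mean is 2.996/17 = 0.176, giving 1.19 (0.79 to 1.81). Not equivalent.

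If both values of a subject are set to the same floor, the CI is 0.83 to 1.21 and the verdict stays equivalent. The handling can decide the verdict but need not.

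**3. How often.** The SAP gives no IPA levels, so everything here is assumed: normal IPA with mean μ in both regimens, between-subject SD 12, within-subject SD 8, 17 pairs. The probability that both records of a subject are positive is p = ∫ φ(b; 0, 12) Φ((μ + b)/8)² db. The chance of at least one IPA ≤ 0 is 1 − p^17, and the expected number of usable pairs is 17p.

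| Mean IPA | Chance of any IPA ≤ 0 | Usable pairs |
|---|---|---|
| 50 | 0.8% | 17.0 |
| 40 | 8.2% | 16.9 |
| 30 | 42% | 16.5 |
| 20 | 90% | 14.8 |

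At mean 30 the chance is 2% with SDs 8/5 and 75% with SDs 15/10.

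**4. How often the handling changes the verdict.** Simulated trials under the same assumptions at true ratio 1, restricted to trials with at least one IPA ≤ 0. A paired log test on complete pairs stands in for the mixed model with the record dropped.

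| Mean IPA | Equivalence shown: deletion | Equivalence shown: 1% floor | Opposite verdicts: 5% floor vs deletion | Opposite verdicts: 1% floor vs deletion |
|---|---|---|---|---|
| 40 | 85% | 25% | 18% | 62% |
| 30 | 49% | 17% | 18% | 37% |
| 20 | 15% | 5% | 10% | 13% |

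Over all trials, multiply by the chance in step 3. Mean 40: 0.082 × 0.18 = 1.5% to 0.082 × 0.62 = 5.1%. Mean 30: 0.42 × 0.18 = 7.6% to 0.42 × 0.37 = 16%. Mean 20: 0.90 × 0.10 = 9% to 0.90 × 0.13 = 12%.

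**5. False equivalence.** At true ratios 0.70 and 1.43, over means 5 to 60 and SD pairs 8/5, 12/8 and 15/10, log analysis with deletion shows equivalence in at most 2.9% of trials, against a nominal 2.5%.

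**The case against.** **The frequency is wholly assumed.** This stands. The SAP's only dispersion figure is 27%, and a fixed within-subject SD of 8 equals 27% only near mean 30. Setting it to 27% of each mean gives 8.9%, 19%, 42% and 81% at means 50, 40, 30 and 20. If IPA is purely multiplicative and positive, as a log model implies, the problem never arises. The gap in the text is certain; its impact is not.

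**The upper flip rates use a harsh floor.** This also stands, which is why ranges are given. With a 5% floor the effect at mean 40 is modest.

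**Section 5.5 forbids imputation, flooring is imputation, so the record simply drops out.** This is a fair reading and it narrows the discretion. But Section 5.5 speaks of missing data, and the value was observed. If deletion is intended, it is a selective exclusion of completers' records that the SAP should state and justify.

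**Low responders stay visible.** True: raw aggregation, descriptive IPA and untransformed IPA are all planned. None of them decides equivalence.

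**The protocol may hold a rule.** It was not at hand. The SAP says in Section 1 that it documents the analysis algorithms and conventions, so a rule for the deciding model belongs in it.

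A reader might also infer that the handling was, or will be, picked to suit the result. The SAP does not show this. The trial is open-label and Section 14 describes dropout in the past tense, which suggests that the SAP was completed after subjects had finished. Nothing says that anyone had seen IPA values, or that any was zero or negative.

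**Conclusion.** The point holds as a gap in the deciding analysis that should be fixed. Sections 6.1 and 11.1.1 together leave the primary model undefined for values the endpoint permits, and Sections 5.4, 5.5, 11.1.1 and 14 do not resolve it. Where such a value occurs, the choice between deletion and a floor reverses the verdict in roughly 10% to 62% of trials, depending on mean IPA and floor. This rests on assumed normal IPA with SDs 12 and 8, 17 pairs and a true ratio of 1. These are conditional rates; over all trials they are about 1.5% to 16% at means 20 to 40.

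A reader might infer that dropping poor responders biases the trial towards equivalence. The calculations do not support that. False equivalence stays near nominal, and deletion attenuates a real rise only at low inhibition: for a true ratio of 1.5 the mixed-model log estimate is 1.30 at reference mean 10, 1.45 at 15 and 1.54 to 1.60 at 20 to 40. The harm is selective loss of observed records, lost precision and room for analyst discretion.

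**What to change.** Before IPA values are examined, add to Section 11.1.1, and by reference to Section 11.2.1:

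> ln(IPA) decides a comparison when all its IPA values are positive. If any IPA ≤ 0 occurs, no record is deleted, floored or offset; equivalence for that comparison rests on the Test/Reference ratio of mean untransformed IPA with a 95% Fieller interval (paired within groups, unpaired between genotypes) against 0.70–1.43. An unbounded interval means equivalence is not shown, and ln(IPA) on positive records is supporting. The number of IPA ≤ 0 values is reported per group, regimen and agonist.

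Record the change in Section 14, and add the Fieller ratio and the count to tables CT-6.1 and CT-6.2.

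The drafting cost is one paragraph, a cross-reference and a Section 14 entry. The statistical costs are these:

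- In comparisons that switch, the estimand becomes a ratio of arithmetic rather than geometric means, so it may differ between comparisons.
- The Fieller interval is imprecise or unbounded when reference IPA is near zero. It was bounded in 98% of simulated trials at mean 15 and 77% at mean 10, and power there is very low with either method.
- Unpaired genotype comparisons of 17 versus 17 have low power either way: Fieller 0.56 against 0.35 for log at mean 40, and 0.13 against 0.06 at mean 30.

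The Fieller test alone showed false equivalence in at most 2.7% of trials. A simulation of the paired switching rule over the means and SD pairs in step 5 stayed within the nominal 2.5%.

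Replacing ln(IPA) in every comparison would go further than the defect requires. It would change the primary estimand throughout and, under multiplicative error with within-subject log-SD 0.27, lower power to 0.82–0.87 from 0.90.

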#### **11.1.2 Platelet Aggregation**

The descriptive statistics of measured values (ie, platelet aggregation) at each timepoint and changes from baseline will be summarized by treatment regimen. Box-plot diagrams will also be provided.

The data on Visit 1 (Day -14 to 0) is defined as baseline for all treatment groups.

### **11.2 Statistical Analyses of Secondary Pharmacodynamics Endpoints**

#### **11.2.1 Inhibition of Platelet Aggregation**

IPA calculated from the light transmission aggregometry in PRP (20  $\mu$ M ADP, residual aggregation at 5 minutes) will also be analysed using the methodology specified in [Section 11.1.1](#).

### **11.2.2 Platelet Aggregation**

For ex-vivo platelet function parameters, the descriptive statistics of measured values (ie, platelet aggregation) at each timepoint and changes from baseline will be summarized by treatment regimen. Box-plot diagrams will also be provided for the following parameters:

- Light transmission aggregometry in PRP (20µM ADP, residual aggregation at 5 minutes)
- Multiplate® (ASPI test, ADP test)
- VetifyNow™ (P2Y12 and Aspirin test)
- VASP by flow cytometry

The data on Visit 1 (Day –14 to 0) is defined as baseline for all treatment groups.

### **11.2.3 Skin Bleeding Time**

Bleeding time at baseline, after monotherapy with cilostazol, aspirin or clopidogrel as well as concomitant treatment of cilostazol plus aspirin and cilostazol plus clopidogrel will also be analysed using the methodology specified in [Section 11.1.1](#). Natural log-transformation will be applied to bleeding time to fit a mixed-effect linear model.

The descriptive statistics of measured values at each timepoint and changes from baseline will be summarized by treatment regimen.

The data on Visit 1 (Day –14 to 0) is defined as baseline for all treatment groups.

## **12 Pharmacogenomic Analyses**

There are no pharmacogenomic analyses in this trial.

## **13 Interim Analysis**

None.

## **14 Changes in Planned Analysis**

The following modification from the statistical analysis specified in the protocol was made.

- A summary of descriptive statistics for ECG values specified in Section 7.3.4 of the protocol will be changed to a shift table of abnormality in ECG findings. ECG values were not collected in this trial.

Protocol 21-13-102

- Sensitivity analysis described in Section 7.1.1 of the protocol will not be conducted. The number of subjects who dropped out of the analysis before finishing the third period was not substantial.

**Appendix 1                      List of Summary Tables**

- CT-1 Subject Disposition
- CT-2 Reasons for Discontinuation
- CT-3.1 Demographic and Baseline Characteristics - Safety Analysis Set
- CT-3.2 Demographic and Baseline Characteristics - Pharmacodynamic Analysis Set
- CT-4 Concomitant Medications
- CT-5.1 Summary of Pharmacodynamic Parameters
- CT-5.2 Summary of Pharmacodynamic Parameters by Genotype
- CT-5.3 Descriptive Statistics for Inhibition of Platelet Aggregation
- CT-5.4 Descriptive Statistics for Skin Bleeding Time
- CT-5.5 Treatment Difference for Inhibition of Platelet Aggregation
- CT-5.6 Treatment Difference for Inhibition of Platelet Aggregation by Genotype
- CT-5.7 Descriptive Statistics for Platelet Aggregation
- CT-6.1 Summary of Pharmacodynamic Parameters - Exploratory Analysis (not Log-transformed Data)
- CT-6.2 Summary of Pharmacodynamic Parameters by Genotype - Exploratory Analysis (not Log-transformed Data)
- CT-7 Extent of Exposure to Investigational Medicinal Product
- CT-8.1 Summary of Adverse Events
  - CT-8.2.1 Incidence of All Treatment-emergent Adverse Events by MedDRA System Organ Class and Preferred Term for Each Treatment Group
  - CT-8.2.2 Incidence of All Treatment-emergent Adverse Events by MedDRA System Organ Class and Preferred Term for Each Treatment Regimen
  - CT-8.3.1 Incidence of Potentially Drug-related Treatment-emergent Adverse Events by MedDRA System Organ Class and Preferred Term for Each Treatment Group
  - CT-8.3.2 Incidence of Potentially Drug-related Treatment-emergent Adverse Events by MedDRA System Organ Class and Preferred Term for Each Treatment Regimen
  - CT-8.4.1 Incidence of Serious Treatment-emergent Adverse Events by MedDRA System Organ Class and Preferred Term for Each Treatment Group

Protocol 21-13-102

CT-8.4.2 Incidence of Serious Treatment-emergent Adverse Events by MedDRA System Organ Class and Preferred Term for Each Treatment Regimen

CT-8.5.1 Incidence of Treatment-emergent Adverse Events Leading to Discontinuation of Investigational Medicinal Product Administration by MedDRA System Organ Class and Preferred Term for Each Treatment Group

CT-8.5.2 Incidence of Treatment-emergent Adverse Events Leading to Discontinuation of Investigational Medicinal Product Administration by MedDRA System Organ Class and Preferred Term for Each Treatment Regimen

CT-8.6.1 Incidence of All Treatment-emergent Adverse Events According to Severity by MedDRA System Organ Class and Preferred Term for Each Treatment Group

CT-8.6.2 Incidence of All Treatment-emergent Adverse Events According to Severity by MedDRA System Organ Class and Preferred Term for Each Treatment Regimen

CT-9.1 Listing of Deaths

CT-9.2 Listing of Serious Adverse Events Other Than Deaths

CT-9.3 Listing of Adverse Events Leading to Discontinuation of Investigational Medicinal Product Administration

CT-10.1.1 Descriptive Statistics for Laboratory Test Results - Serum Chemistry

CT-10.1.2 Descriptive Statistics for Laboratory Test Results - Hematology and Coagulation

CT-10.1.3 Descriptive Statistics for Laboratory Test Results - Urinalysis

CT-10.2.1 Shift Table of Laboratory Test Results - Serum Chemistry

CT-10.2.2 Shift Table of Laboratory Test Results - Hematology and Coagulation

CT-10.2.3 Shift Table of Laboratory Test Results - Urinalysis

CT-10.3.1 Shift Table of Laboratory Test Results - Qualitative Urinalysis (1)

CT-10.3.2 Shift Table of Laboratory Test Results - Qualitative Urinalysis (2)

CT-10.4 Listing of Abnormal Laboratory Findings

CT-10.5 Listing of Potential Hy's Law Cases

CT-11.1 Descriptive Statistics for Vital Signs

CT-11.2 Descriptive Statistics for Body Weight

CT-12 Shift Table of Electrocardiogram Findings

**Appendix 2**                    **List of Summary Figures**

CF-1 Confidence Interval of Inhibition of Platelet Aggregation

CF-2 Box Plot of Platelet Aggregation

**Appendix 3                      List of Subject Data Listings**

DREAS-1 Discontinued Subjects and Reason for Discontinuation

SUBEX-1 Subjects Excluded From Analysis Set

DEMOG-1 Demographic Characteristics

SMED-1 Investigational Medicinal Product Compliance

AE-1 Adverse Events

LAB-1 Laboratory Test Results - Serum Chemistry

LAB-2 Laboratory Test Results - Hematology and Coagulation

LAB-3 Laboratory Test Results - Urinalysis

PDATA-1 Study Completion Status and Reason for Discontinuation

PDATA-2 Medical History and Current Symptoms

PDATA-3 Prior and Concomitant Medications

PDATA-4 Concomitant Therapy

PDATA-5 Vital Signs and Body Weight

PDATA-6 Electrocardiogram Results

PDATA-7 Platelet Aggregation - Primary Outcome Variables

PDATA-8 Platelet Aggregation - Secondary Outcome Variables

PDATA-9 Skin Bleeding Time

PDATA-10 Screen Failures

PDATA-11 Drug Screen, Alcohol Screen and Infectious Disease Test Results

PDATA-12 Physical Examination

PDATA-13 Drug Accountability
